#### **10.3.1.1. Serious Adverse Events**

An SAE is any AE from this study that results in 1 of the following outcomes:

- death
- life-threatening experience (that is, immediate risk of dying)
- persistent or significant disability/incapacity
- initial or prolonged inpatient hospitalization
- congenital anomaly/birth defect
- considered significant by the investigator for any other reason

Important medical events that may not result in death, be life-threatening, or require hospitalization may be considered serious adverse drug events when, based on appropriate medical judgment, they may jeopardize the patient and may require medical or surgical intervention to prevent one of the outcomes listed in this definition.

SAE collection begins after the patient has signed informed consent and has received study drug. If a patient experiences an SAE after signing informed consent, but prior to receiving study drug, the event will not be reported as serious unless the investigator feels the event may have been caused by a protocol procedure.

SAEs occurring after a patient has taken the last dose of study drug will be collected for 30 days after the discontinuation from study treatment, regardless of the investigator’s opinion of causation. Thereafter, SAEs are not required to be reported unless the investigator feels the events were related to either the study drug, the drug delivery system, or a protocol procedure.

Study site personnel must alert Lilly or its designee of any SAE within 24 hours of investigator awareness of the event via a sponsor-approved method. If alerts are issued via telephone, they are to be immediately followed with official notification on study-specific SAE forms.

This 24-hour notification requirement refers to the initial SAE information and all follow-up SAE information.

Planned surgeries should not be reported as SAEs unless the underlying medical condition has worsened during the course of the study.

Planned hospitalizations or procedures for preexisting conditions that are already recorded in the patient's medical history at the time of study enrollment should not be considered SAEs. Hospitalization or prolongation of hospitalization without a precipitating clinical AE (for example, for the administration of study therapy or other protocol-required procedure) should not be considered SAEs.

SAEs due to disease progression, including death, should not be reported unless the investigator deems them to be possibly related to the study drug.

If an investigator becomes aware of an SAE occurring after the patient's participation in the trial has ended, and the investigator believes that the SAE is related to a protocol procedure or study drug, the investigator should report the SAE to the sponsor, and the SAE will be entered in the pharmacovigilance system at the sponsor.

Information on SAEs expected in the study population independent of drug exposure and that will be assessed by the sponsor in aggregate periodically during the course of the trial may be found in the IB.

#### **10.3.1.2. Suspected Unexpected Serious Adverse Reactions**

Suspected unexpected serious adverse reactions (SUSARs) are serious events that are not listed in the DCSI in the IB and that the investigator identifies as related to the investigational product or study procedure. US 21 Code of Federal Regulations 312.32 and EU Clinical Trial Directive 2001/20/EC and the associated detailed guidances or national regulatory requirements in participating countries require the reporting of SUSARs. Lilly has procedures that will be followed for the recording and expedited reporting of SUSARs that are consistent with global regulations and associated detailed guidances.

#### **10.3.2. Other Safety Measures**

##### **10.3.2.1. Electrocardiography**

For each patient, 12-lead digital ECGs will be obtained as single ECGs according to the Study Schedule ([Attachment 1](#)). Patients must be supine for approximately 5 to 10 minutes before ECG collection and remain supine during ECG collection. ECGs may be obtained at additional times when deemed clinically necessary. Collection of more ECGs than expected at a particular time point is allowed when needed to ensure high-quality records.

ECGs will be interpreted by a qualified physician (the investigator or qualified designee) at the site as soon after the time of ECG collection as possible, and ideally while the patient is still present, to determine whether the patient meets entry criteria and for immediate patient management, should any clinically relevant findings be identified.

If a clinically significant quantitative or qualitative change from baseline is identified after enrollment, the investigator will assess the patient for symptoms (for example, palpitations, near

syncope, syncope) and to determine if the patient can continue in the study. The investigator or qualified designee will be responsible for determining if any change in patient management is needed and must document his/her review of the ECG printed at the time of evaluation.

All digital ECGs will be electronically transmitted to a central ECG laboratory designated by Lilly. A cardiologist at the central ECG laboratory will then conduct a full overread on the ECG (including all intervals); a report based on data from this analysis will be issued to the investigative site. All data from the overreads will be placed in the Lilly database for analytical and study-report purposes.

It is recognized that ECG interpretations by the investigator (or qualified designee) and by the cardiologist at the central ECG laboratory may be different. When there are differences in ECG interpretation between the investigator (or qualified designee) and the cardiologist at the central ECG laboratory, the investigator (or qualified designee) interpretation will be used for study entry and immediate patient management. Interpretations from the cardiologist at the central ECG laboratory will be used for data analysis and report-writing purposes.

The investigator (or qualified designee) must document his/her review of the ECG printed at the time of evaluation, the final overread ECG report issued by the central ECG laboratory, and any alert reports.

Other safety measures include assessments of physical examinations, preexisting conditions, transfusions and hospitalizations, and AEs. Patients will be assessed before each visit by using the CTCAE version 4.0.

For patients in the extension period, monitoring should be performed at predose on Day 1 of every other cycle for patients receiving galunisertib. The standard care of treatment should be followed for patients receiving sorafenib.

#### **10.3.2.2. Echocardiographs with Doppler and Chest Computed Tomography Scans**

Because of the cardiotoxicity monitoring in this study, echocardiographs with Doppler and chest CT scans are being performed (see [Attachment 1](#), [Attachment 14](#), and [Attachment 15](#)).

Echocardiography with Doppler will be locally assessed at screening for enrollment and throughout the study according to the Study Schedule ([Attachment 1](#)) for safety decisions by a physician or a person who is qualified by experience or training. The individual must be identified at each site. A central reading will be performed for the data used in the study report.

Chest CT scan with contrast of thorax and abdomen to evaluate the large vessels of the heart will be locally assessed at screening for enrollment and every 6 months throughout the study and at the end of study visit (Visit 801) according to the Study Schedule ([Attachment 1](#)) for safety decisions by a physician or a person who is qualified by experience or training. Alternatively, chest and/or abdomen MRI are allowed.

Chest CT scan with contrast of thorax and abdomen for tumor assessment will be locally assessed at screening for enrollment and every 6 weeks starting Cycle 2 Day 14 until radiological disease progression according to the Study Schedule ([Attachment 1](#)) by a physician or a person

who is qualified by experience or training. Alternatively, chest and/or abdomen MRI are allowed.

If the patient has clinically significant cardiac findings at discontinuation (Visit 801), echocardiography, ECG and ECG chemistry will be repeated every 2 months for 6 months (Visits 803, 804, and 805).

If there are no clinically significant cardiac findings at discontinuation (Visit 801), 1 more echocardiography, ECG, and ECG chemistry will be performed after 2 months (Visit 802). If a patient receives another treatment, Visit 802 cardiac assessments will not be performed.

For cardiac monitoring of patients in the extension period, chest CT scan or MRI will be locally assessed every 6 months for patients receiving galunisertib. Tumor and radiological assessments are recommended at regular intervals during the extension period. The rest of the monitoring described in the previous 2 paragraphs will also be applicable for patients in the extension period. Therefore, for these cases, the patient does not discontinue from the study at the end of the 30-day safety follow-up period but after the cardiac findings have either resolved or, if not resolved after 6 months, after discussions between the Lilly CRP and investigator.

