## 10. Efficacy, Health Outcome/Quality of Life Measures, Safety Evaluations, Sample Collection and Testing, and Appropriateness of Measurements

Terms used to describe the periods during the study are defined below:

- **Baseline (Visit 0):** From the time of screening to the first study treatment (or discontinuation, if no treatment is given)
- **Treatment Start:** First day of study treatment
- **Treatment Period:** Time from treatment start to discontinuation from study treatment
  - During the study period, cycle number will correspond to visit number (eg, Cycle 1 = Visit 1).
  - During the extension period, cycle number will correspond to extension visit number (eg, Cycle 1 = Visit 501).
- **Discontinuation from Study Treatment:** The day the patient discontinues study treatment (summary visit)
  - applies to patients in extension period, too
- **30-Day Safety Follow-Up Period (Visit 801):** The time after the patient discontinues study treatment during which follow-up data are collected. Visit 801 starts 1 day after discontinuation from study treatment and lasts 30 days ( $\pm 3$  days).
  - applies to patients in extension period, too. However, for patients in the extension period, the end of the 30-day safety follow-up period is also the end of their study participation (unless further follow-up is required for cardiac toxicities).
- **Long-Term Follow-Up Period (Visits 802, 803, etc):** Visit 802 starts 1 day after the 30-day Safety Follow-up (Visit 801) and lasts 60 days ( $\pm 7$  days). All subsequent long-term follow-up visits will occur at 60-day intervals ( $\pm 7$  days) (for example, Visit 803, Visit 804, etc.) for as long as the patient remains alive or until the required number of deaths have been observed.
  - not required for patients in extension period unless there are cardiac toxicities

Written informed consent must be obtained prior to any study-specific pretreatment evaluations.

Study procedures related to efficacy, safety, health outcome/quality of life measures, sample collection and testing assessments and their timing are described in the sections below and are shown in the Study Schedule ([Attachment 1](#)).

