- i If the patient has clinically significant cardiac findings at discontinuation (Visit 801), echocardiography with Doppler and ECG and ECG chemistry will be repeated every 2 months for 6 months (Visits 803, 804, and V805). If there are no cardiac findings at discontinuation (Visit 801), 1 more echocardiography with Doppler, ECG, and ECG chemistry will be performed after 2 months (Visit 802) unless a patient is receiving another treatment (see Section [10.3.2.2](#)).
- j If there were no clinically significant findings at the last assessment conducted within the 30 days following discontinuation and the patient has started another treatment, Visit 801 CT scan or chest MRI with contrast will not be performed.
- k Repeat radiological scans at study discontinuation may be omitted if a patient has objective disease progression or if imaging has been performed in the previous 3 to 6 weeks.
- l Within 60 days prior to randomization; includes HBsAg, hepatitis B surface antibody, total hepatitis B core antibody, hepatitis B e antigen, hepatitis B e antibody, hepatitis B virus DNA, hepatitis C RNA.
- m HBsAg carriers should be closely monitored with assessment of hepatitis B serology during the study treatment and 30-day safety follow-up period.
- n  $\pm$ 3 days after end of treatment with LY2157299.

Study Schedule, Protocol H9H-MC-JBAS: Extension Period

Cycle (Visit)	Study Treatment (v501, v502, etc) a	Post Discontinuation Follow-Up Periods		Comments
		30-day Safety Follow-Up (v801)	Long-Term Follow-Up b (v802)	
Refer to Section 10 of the protocol for descriptions of the study periods				
Procedures				
Physical exam	X	X		Performed once per cycle on Day 1 of each cycle in extension period
Vital signs (heart rate, blood pressure, weight)	X	X		Performed once per cycle predose on Day 1 of each cycle in extension period
CTCAE grading	X	X	X c	Performed once per cycle predose on Day 1 of each cycle in extension period
Concomitant medications	X	X	X	Performed once per cycle predose on Day 1 of each cycle in extension period
Performance status	X	X		Performed once per cycle predose on Day 1 of each cycle in extension period
Imaging procedures				
Echocardiography with Doppler d	X	X e	X e	For patients receiving galunisertib: Performed once per cycle predose on Day 1 of every other cycle in the extension period.

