Chest CT scan or chest MRI	X	X f		For patients receiving galunisertib: CT scan or MRI every 6 months (for cardiac assessment).
Tumor assessment, radiological				Recommended at regular intervals during the extension period.
ECG	X	X e	X e	For patients receiving galunisertib: Perform predose on Day 1 of every other cycle in the extension period. For patients receiving sorafenib only, follow standard of care.

Cycle (Visit)	Study Treatment (v501, v502, etc.) a	Post Discontinuation Follow-Up Periods		Comments
		30-Day Safety Follow-Up (v801)	Long-Term Follow-Up b (v802)	
				Refer to Section 10 of the protocol for descriptions of the study periods
Laboratory tests				
Hepatitis B serology	X g	X g		HBsAg carriers only. Can be done at local labs during the extension period.
ECG chemistry	X	X e	X e	For patients receiving galunisertib: Perform predose on Day 1 of every other cycle in the extension period. Can be done at local labs during the extension period. For patients receiving sorafenib only, follow standard of care.
Special chemistry	X	X		For patients receiving galunisertib: Perform predose on Day 1 of each cycle in the extension period. Can be done at local labs during the extension period. Includes troponin and BNP. For patients receiving sorafenib only, follow standard of care.
Hematology	X	X		Perform predose on Day 1 of each cycle in extension period. Can be done at local labs during the extension period
Serum chemistry	X	X		Perform predose on Day 1 of each cycle in extension period. Can be done at local labs during the extension period
Serum markers	AFP only	X		As clinically indicated. Can be done at local labs during the extension period.

Abbreviations: BNP = brain natriuretic peptide; CT = computed tomography; CTCAE = Common Terminology Criteria for Adverse Events; ECG = electrocardiogram; exam = examination; HBsAg = hepatitis B surface antigen; MAP = multi-analyte panel; MRI = magnetic resonance imaging; v = visit.

- a A delay at the start of a cycle (Day 1) of no more than 3 days because of holidays, weekends, inclement weather, or other justifiable events will be permitted and not counted as a protocol violation.
- b Follow-up consists of Visit 802 and all subsequent visits (60 days $\pm$ 7 days). For the patients in the extension period, long-term follow-up will not be conducted unless there are cardiac toxicities (Section 10.3.2.2).

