- c If drug-related toxicity is present 30 days after last cycle of study drug, patients must be followed up approximately every 30 days until toxicity resolution, stabilization, another therapy is initiated, or death.
- d Echocardiography with Doppler can be performed up to 3 days prior to Day 1.
- e If the patient has clinically significant cardiac findings at discontinuation (Visit 801), echocardiography with Doppler and ECG and ECG chemistry will be repeated every 2 months for 6 months (Visits 803, 804, and V805). If there are no cardiac findings at discontinuation (Visit 801), 1 more echocardiography with Doppler, ECG, and ECG chemistry will be performed after 2 months (Visit 802) unless a patient is receiving another treatment (see Section 10.3.2.2).
- f If there are no clinically significant findings at the last assessment conducted within the 30 days following discontinuation and the patient has started another treatment, Visit 801 CT scan or chest MRI with contrast will not be performed.
- g HBsAg carriers should be closely monitored with assessment of hepatitis B serology during the study treatment and 30-day safety follow-up period.

Study Schedule, Protocol H9H-MC-JBAS – Study Drug Dosing

Cycle (Visit)	Study Period		Extension Period (Visits 501, 502, etc.)		Comments
	Cycle 1, n (Visit 1, n)				
Relative Day Within a Cycle	1-14	15-28	1-14	15-28	Refer to Section 10 of the protocol for descriptions of the study periods
LY2157299 dosing	X		X		The monotherapy dose will be 150 mg BID (300-mg daily dose) for 14 days, followed by 14 days with no study drug. The LY2157299 dose used in combination with sorafenib will be determined based on the results of the JBAK study – Part C (dose will either be 80 mg or 150 mg BID [160-mg or 300-mg daily dose]).
LY2157299-matched placebo dosing	X				Administered orally by daily dosing morning and evening (BID) for 14 days, followed by 14 days with no placebo. Not administered in the extension period
Sorafenib	X	X	X	X	Administered orally by daily dosing morning and evening (BID) at 400 mg per dose (total dosage of 800 mg daily) for 28 days

Abbreviation: BID = twice daily.

---

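### Cardiac rechecks for patients with findings at Visit 801 are printed as Visits 803–805, but the stated two-monthly schedule over six months is Visits 802–804

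*Protocol*

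**What the plan says.** Protocol Section 10.3.2.2 gives two rules for cardiac follow-up after treatment stops.

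- Patients with clinically significant findings at Visit 801: echocardiography, ECG and ECG chemistry "will be repeated every 2 months for 6 months (Visits 803, 804, and 805").
- Patients without such findings: "1 more echocardiography, ECG, and ECG chemistry will be performed after 2 months (Visit 802"). A separate sentence then waives the Visit 802 cardiac assessments if the patient receives another treatment.

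The first rule carries the same visit numbers in Attachment 1, study-period footnote i ("repeated every 2 months for 6 months (Visits 803, 804, and V805"), in Attachment 1, extension-period footnote e ("ECG and ECG chemistry will be repeated every 2 months for 6 months (Visits 803, 804, and V805"), and in SAP Section 6.12.7.

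Protocol Section 10 defines the visits: "Visit 802 starts 1 day after the 30-day Safety Follow-up (Visit 801) and lasts 60 days", with a 7-day allowance either way, and "All subsequent long-term follow-up visits will occur at 60-day intervals", with the same allowance.

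For extension patients with cardiac findings, Section 10.3.2.2 ends participation once the findings have resolved or, "if not resolved after 6 months, after discussions between the Lilly CRP and investigator". Extension-period footnote b adds that "long-term follow-up will not be conducted unless there are cardiac toxicities".

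**The concern.** The interval and the visit numbers in the first rule do not describe the same dates. If Visit 802 is two months after Visit 801, a two-monthly series over six months starts at Visit 802 and ends at Visit 804. The printed series starts and ends one visit later.

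Sites schedule by visit number. Followed literally, the rule gives patients with a cardiac finding their first mandated recheck one visit after patients with no finding, and puts their last one beyond the six-month point in the extension rule. In the extension period the result is odder still: long-term follow-up exists there only because of cardiac toxicity, yet its first visit would carry no cardiac assessment for those patients.

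The heart and great vessels are a main target organ in the nonclinical studies (Protocol Section 5.1.4), and moderate or severe valve toxicity requires immediate discontinuation (Section 9.4.1.1), so some patients may reach Visit 801 with findings. SAP Appendix 1 also treats ECG and echocardiography not done under Attachment 1 as significant violations. Checked by visit number, a missing Visit 802 recheck would go unflagged, while a missing Visit 805 assessment, outside the stated six months, would be flagged.

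**Working it through.** **Inputs.** The 60-day spacing and the ±7-day allowance come from Protocol Section 10. The anchor, Visit 802 at two months, comes from Section 10.3.2.2. A month is taken as 30.44 days, so six months = 6 × 30.44 = 182.6 days.

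**Visit dates, counted from the end of Visit 801.** Day of Visit V = 60 × (V − 801). With n = V − 801 intervals, the window is ±7 days, or ±7n if the allowances accumulate.

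| Visit | Day | Months (day ÷ 30.44) | Window ±7 | Window if accumulated |
|---|---|---|---|---|
| 802 | 60 | 2.0 | 53–67 | 53–67 |
| 803 | 120 | 3.9 | 113–127 | 106–134 |
| 804 | 180 | 5.9 | 173–187 | 159–201 |
| 805 | 240 | 7.9 | 233–247 | 212–268 |

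**Comparison with the stated schedule.** Months 2, 4 and 6 match Visits 802, 803 and 804. The printed Visits 803, 804 and 805 fall at about months 4, 6 and 8, so the stated interval is not reproduced.

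- First recheck: day 120 instead of day 60, a shift of 60 days.
- Last recheck: day 240 instead of day 180, also 60 days.

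**Can the windows absorb this?** No. The latest Visit 802 is day 67. The earliest Visit 803 is day 113, or day 106 with accumulation, which leaves at least 106 − 67 = 39 days. The earliest Visit 805 is day 233, or day 212 with accumulation, at least 212 − 183 = 29 days past six months.

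**Alternative dating.** Suppose each visit is dated at the opening of its 60-day period: day = 1 + 60 × (V − 802). Visits 803, 804 and 805 then fall on days 61, 121 and 181, which fits the printed numbers. Visit 802, however, falls on day 1, which contradicts the next rule's placement of Visit 802 at two months. No single convention satisfies both rules.

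**The case against.** The strongest counter-argument is that Section 10 describes Visit 802 as a period rather than a date. If later visits are periods too, Visit 802 closes on day 60 and Visit 803 opens on day 61, so Visits 803 to 805 could open at months 2, 4 and 6. It stands to this extent: the 60-day delay depends on dating visits at the end of their periods. But that is the only dating under which the rule for patients without findings makes sense, and reading the two adjacent rules under different conventions has no basis in the text.

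Second, the Attachment 1 grids mark echocardiography, ECG and ECG chemistry in long-term follow-up, and the extension grid heads that column with Visit 802 alone. Together with the plain interval, this may lead some sites to do the right thing. The marks, however, carry footnotes i and e, which assign Visit 802 only to patients without findings.

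Third, the extension rule prevents release of unresolved patients before six months; it does not fix a meeting at month 6, so an assessment at Visit 805 would not breach it. That is fair, but the stated duration of the rechecks is still six months.

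Fourth, one could add Visit 802 and keep the other three. That closes the gap but runs to about month 8, past the stated six months. It would be a new design decision, not a correction.

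Finally, there are backstops. Serious, study-related or discontinuation-causing adverse events are followed until resolved or explained (Section 10.3), drug-related toxicity is followed about every 30 days (Attachment 1), and extra ECGs are allowed (Section 10.3.2.1). These limit the harm, but none mandates an echocardiogram.

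**Conclusion.** The rule is wrong as written. On the plan's own anchor for Visit 802, the printed numbers place every recheck one visit, or 60 days, later than the stated interval. That the number of visits is right and only the labels are shifted points to a numbering slip.

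The practical reach is probably small. Protocol Section 5.1.5 reports no cardiovascular toxicity among 218 patients enrolled in trials of the drug, and the documents do not allow an estimate of how many patients in this trial would have findings at Visit 801. Some sites may follow the words rather than the numbers. Sample size, power and the overall survival analysis are unaffected. It still deserves correction: it is an operative safety rule, and followed by visit number it gives patients with cardiac findings a later recheck than patients without them.

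**What to change.** Print Visits 802, 803 and 804 in place of Visits 803, 804 and 805 in four places: Protocol Section 10.3.2.2, Attachment 1 footnote i (study period), Attachment 1 footnote e (extension period), and SAP Section 6.12.7.

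In Section 10.3.2.2, also state that the waiver of Visit 802 cardiac assessments for patients who receive another treatment applies only to patients without findings. Footnotes i and e already word it that way. Left free-standing, the sentence could, after renumbering, remove the first recheck from patients with findings. SAP Section 6.12.7 carries the same free-standing sentence and should be aligned.

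The cost is wording only. Visit 802 already exists for these patients, and one set of assessments moves from Visit 805 to Visit 802.
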